Impact of Neurobiological Substrates of Social Stress in
Individuals with Alcohol Use Disorder

NCT03610633

Version Date: January 4, 2018

Impact of Oxytocin on Neurobiologic Substrates of Social Stress in Individuals with Alcohol Use Disorder

[figure not shown]
Social stress is an important factor in the motivation to use and abuse alcohol, and social avoidance is a symptom of alcohol dependence [1, 2]. Social avoidance also impedes effective treatment particularly in group settings that are a commonly employed treatment modality. Data from human neuroimaging studies suggest that functional connectivity between the prefrontal cortex and limbic brain regions is important for maintaining affective and behavioral responses to social stimuli while results from clinical and preclinical studies suggest that chronic alcohol exposure produces alterations in corticolimbic brain regions that may underlie compulsive drug seeking behavior and relapse [3-6]. Therefore, therapeutic interventions that increase corticolimbic connectivity may be effective at ameliorating reactivity to social stress and reducing craving in alcohol dependent individuals. The neuropeptide oxytocin (OT) increases social approach, trust, and reduces anxiety to social stress [7-9]. Data from recent studies show that OT administration restored corticolimbic connectivity in individuals with social anxiety disorder and decreased withdrawal symptoms in alcohol dependent individuals [10, 11]. In addition, OT attenuated drug craving and anxiety in marijuana-dependent individuals exposed to a social stress task [12]. In this project, we propose a double-blind placebo controlled pilot study to compare the impact of OT versus placebo on corticolimbic connectivity in alcohol dependent subjects. Blood oxygen level dependent (BOLD) functional magnetic resonance imaging (fMRI) will be used to measure corticolimbic connectivity at rest and during the Montreal Imaging Stress Task (MIST) [13]. Subjective craving and anxiety data will also be collected. Prior to the scanning session, participants will receive either intranasal OT (24 IU) or a placebo (PBO) spray.

Aim 1: Determine the impact of OT on corticolimbic connectivity in alcohol dependent individuals exposed to social stress. Psychophysiological interaction (PPI) analysis using the amygdala as the seed region will be used to assess significant task (stress condition > control condition) x seed interactions. Hypothesis 1A: The OT group will exhibit greater functional connectivity between the amygdala and prefrontal cortical regions (orbitofrontal and anterior cingulate cortices) than the PBO group. Hypothesis 1B: The OT group will report lower subjective anxiety and craving in response to the MIST than the PBO group.

Aim 2: To determine the impact of OT on resting-state functional connectivity in alcohol dependent individuals. Hypothesis 2A: OT will modulate resting-state functional connectivity among sub-networks implicated in reward and motivation (nucleus accumbens, and orbitofrontal cortex), memory and learning (amygdala and hippocampus), and cognitive control (prefrontal cortex and anterior cingulate cortex).

Preliminary Data: Evidence for Corticolimbic Uncoupling During Social Stress in Individuals with SUDs

We examined corticolimbic coupling during the MIST in cocaine-dependent (DSM-4) (n=13) and healthy control (n=15) subjects using a psychophysiological interaction (PPI) analysis. Using the left amygdala as the seed region, significant task x seed interactions were found in both groups (**Figure 1A**). In the cocaine-dependent group, the left amygdala exhibited significantly greater functional connectivity with the posterior cingulate cortex during stress. In the control group, the left amygdala exhibited significantly greater functional connectivity with the orbitofrontal cortex during stress. The MIST produced a significantly greater increase in anxiety in cocaine-dependent individuals than healthy controls (**Figure 1B**). These data provide support and lend feasibility to employing these imaging and stress task procedures in this proposed pilot project.

Approach:

Participants: Twenty-four individuals with AUD will be recruited through the Clinical Intake and Assessment (CIA) Core of the ARC. Screening and basic assessments will be conducted by the CIA Core to determine eligibility and suitability for participation in this pilot project. Each individual will sign an IRB-

approved informed consent form. ***Inclusion criteria*** include: 1) male or female, any race or ethnicity; ages 21-40, 2) able to comprehend English and function at an intellectual level sufficient to provide informed consent and complete the assessments, 3) meet DSM-5 criteria for current alcohol use disorder and reports drinking on average, at least 20 standard alcoholic drinks per week for at least the past three months, 5) not engaged in and does not want treatment for alcohol related problems, 6) lives within a 50 mile radius of the ARC, and 7) able to maintain abstinence from alcohol for the two days prior to the study visit. ***Exclusion criteria*** include: 1) meet DSM-5 criteria for any other psychoactive substance use disorder, 2) psychoactive substance use (except marijuana and nicotine) within the last 30 days, 3) meet DSM-5 criteria for current major depression, panic disorder, obsessive-compulsive disorder, post-traumatic stress syndrome, bipolar affective disorder, schizophrenia, dissociate disorders, eating disorders, and any other psychotic disorder or organic mental disorder, 4) women who are pregnant or breastfeeding, 5) current suicidal ideation or homicidal ideation, 6) taking psychoactive medications or medications known to affect alcohol intake, 8) history of/or current cardiovascular, renal, GI, neurological or endocrine diseases, 9) history of alcohol related illness, 10) SGPT (ALT) or SGOT (AST) levels greater than 2.5 times normal at screening, 11) charges pending for a violent crime, 12) an unstable living situation, 13) presence of ferrous metal in the body, 14) claustrophobia or morbid obesity, and 15) history of head injury with >2 minutes of unconsciousness.

Study Visit Assessments: The Drinking Motives Questionnaire Revised will be used to assess motivation for drinking across four subscales: (1) coping motives; (2) social motives; (3) conformity motives; and (4) enhancement motives [14]. The Form 90 will be used to assess daily alcohol consumption in the 90 days prior to the study visit and the time from last drink [15]. A modification of the Within Session Rating Scale will be used to assess craving and mood [16]. The Childhood Trauma Questionnaire (CTQ) will be used to assess trauma prior to age 18 [24]. To determine MRI safety, the Metal Screening Questionnaire (MSQ) will be filled out by each participant and reviewed by study staff. To assess potential alcohol withdrawal symptoms, the Clinical Institute Withdrawal Assessment of Alcohol Scale, Revised (**CIWA-Ar**) will be administered [30].

Study Visit Procedures: Participants will be asked to arrive at the Addiction Sciences Division on the study visit day. Female participants will have their urine tested for pregnancy. Females who test positive for pregnancy will be excluded. All participants will be tested for drugs of abuse and alcohol. Patients testing positive for drugs, with the exception of marijuana, will be excluded; patients testing positive for alcohol may be re-scheduled. Participants who have not had a physical exam in the Addiction Sciences Division within the last 30 days will have and H&P. Participants will be asked about substance use in the last 90 days and will fill out the Drinking Motives Questionnaire, the CTQ, and the MSQ. They will then be escorted to the scanner at [name].

The study will use a double-blind placebo controlled design. Intranasal OT (n=12) or PBO (n=12) sprays will be administered at 11:30 am, approximately 45 min prior to the scanning session. This dose and timing of OT administration were selected based on the literature [17, 18]. ***MIST Procedure:*** The study will use a block design of three, 6-min runs separated by 2-min of rest for feedback, for a total of 24 min. During each run, participants will be exposed to 40-sec blocks of three different conditions (rest, control, and experimental). Prior to the task, participants will be shown images of what the screen will look like during each condition. The participants will be instructed to relax during the rest condition and focus on the screen. During the control condition, the participants will be asked to answer math problems as accurately as possible but will also be told that their responses will not be recorded. During the experimental condition, the participants will be asked to perform the math task as quickly and accurately as possible. A performance bar located on the screen will allow them to see their performance as compared to an “average” person. The participants will be told that the average person would answer about 85% of the problems correctly; however, the program limits the participants’ performance rate to between 35-45%. A time limit will be enforced throughout the experimental condition. After each run, the participants will be given negative feedback from the investigator. ***BOLD-fMRI Procedure:*** Data will be acquired on a Siemens Trio 3T scanner in MUSC’s Center for Biomedical Imaging. For co-registration and normalization of functional images, a high resolution T1-weighted MPRAGE anatomical image will be acquired with the following parameters: TR= 2100 ms, TE= 4.18 ms, flip angle= 12°, field of view= 256 mm, slice thickness= 1.0 mm. The scanning planes will be oriented parallel to the anterior commissure–posterior commissure line. Participants will be asked to relax and keep their eyes opened and fixed on a cross-hair for 6 min while resting state data are collected. Participants will then complete the MIST. T2*-weighted gradient-echo planar images (EPI) will be acquired with the following parameters: TR= 2000 ms, TE= 27 ms, flip angle= 76°, matrix 64 x 64, field of view= 23 cm, slice thickness= 3.7 mm with no gap, with 36 slices to cover the entire

brain. ***Implicit Facial Affect Recognition Task:*** The amygdala response to emotional faces that are presented outside the focus of attention (i.e. implicit tasks) is significantly greater than that observed during overt (explicit) presentation of the same stimuli [25]. Emotional adult faces will be selected from a variety of sources are standardized in size and enclosed in the same oval surround [26]. [name] (MUSC) has developed a corpus of faces for a recent project (National Institute of Mental Health, R21 MH086958-01, “A comparative developmental connectivity study of face processing”) that will be used for the present project. The faces will depict male and female Caucasian, Asian and African Americans expressing three different categories of emotion; fear, anger, and happiness. Neutral faces will also be presented (Figure 5). Because the participants will also be from different ethnic categories, it is important to include a mixture of races. In a block design, participants will view a series of faces (for 27.5 sec) within a block and report on the gender of those faces at the end of the block (for 5 sec). Each block will present 56 faces that depict the same emotion and same gender so there will be 6 pseudorandomly ordered task blocks (3 emotions x 2 genders) and 7 rest blocks (27.5 sec each) that present a crosshair to be fixated. In each task block, each emotional face will be presented for 33 msec. followed by a neutral face mask (from a different individual) for 167 msec. followed by a blank screen for 291 msec. At the end of the block participants will report the gender using two buttons on a response pad. Assignment of face sets to sessions will be counterbalanced across subjects.

Payment to Participants: Participants will receive \$100 for completing the scanning visit.

Data Analyses *MIST:* Post-acquisition preprocessing and statistical analysis of all of imaging data will be performed using FEAT (FMRIB Expert Analysis Tool) Version 5.98, part of FSL (FMRIB's Software Library). Data will be preprocessed using scripting tools from FMRIB Expert Analysis Tool (FEAT). Functional connectivity will be measured using a PPI seed-based approach [19]. A customized square wave-form representing the task and the duration of each condition will be convolved with a double-gamma hemodynamic response function. A mask of the seed region will be made using a 12-mm diameter sphere located in the center of the amygdala using the MNI coordinates (x, y, z = ±22, 0, -22). For each participant, the mean corrected and high pass filtered time series of the BOLD signal in the amygdala will be extracted and used in a single subject whole brain PPI analysis. The PPI model will include (1) the task vector; (2) the time series of the BOLD signal in the amygdala; (3) a term representing the positive task x seed interaction; and (4) a term representing the negative task x seed interaction. The first level analysis will generate contrast images of the parameter estimates for each of the four regressors. Since the hypotheses explore increases in corticolimbic connectivity, the group analysis will focus on the positive interaction term. The contrast images of the parameter estimates of the positive interaction term will be entered into a 2nd level random effects analysis. Unpaired t-tests will be used to test for group differences. All group level results will be thresholded at $Z > 2.3$ using a corrected cluster threshold of $p = 0.05$. A linear mixed effects model containing all serially measured time points will be used to assess the effects of OT versus placebo on alcohol craving and anxiety ***Implicit Facial Affect Recognition Task:*** Following preprocessing (described above), within-task data from individual participants will be analyzed with a fixed-effects general linear model (GLM), with each emotion (described below) modeled as a box-car function convolved with a double-gamma hemodynamic response function. The response period at the end of each block will also be modeled as a separate variable to remove effects of explicit decision making and response selection. The GLM procedure is repeated for each voxel with six movement parameters (3 rotation values in radian and 3 translation values in millimeter) included as covariates to control for the influence of head motion on the data. Following first-level analysis, subject-specific contrasts will be entered into second-level, random-effects analyses. Since the hypotheses associated with Specific Aim 2 explore amygdala activity, we will use a region of interest approach (ROI). The BOLD signal from the left amygdala will be extracted using an anatomical mask generated by a 12-mm diameter sphere located in the center of the left amygdala using the MNI coordinates (x, y, z = -22, 0, -22). The percent signal change between the fearful and neutral conditions (contrast of interest) will be calculated for each participant. Separate random-effects one-way analysis of variance tests (ANOVA) will be used to test for the following group differences (AUD-PBO vs. AUD-OT). Since human neuroimaging studies have found that other brain regions play a role in implicit emotional processing, including the right amygdala and insula [27,28], secondary analyses will also include these regions. In addition, OT may impact amygdala responding to happy faces [29] therefore group differences in amygdala responding in the happy-neutral contrast may be explored in future

analyses. For multiple comparisons that are not part of the hypothesis a priori, the Bonferroni correction will be used. In addition, contrasts of other pertinent baseline characteristics will be performed between groups. If the groups differ significantly on any of these baseline characteristics, the corresponding variables will be used as covariates in the above analyses. The statistical analyses will be conducted using SAS 9.3 software (SAS Institute Inc., Cary, NC, USA).

PROTECTION OF HUMAN SUBJECTS

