1. RISKS TO THE SUBJECTS

1.1 Human Subject Involvement and Characteristics

Admission into the study is open to men and women and to all racial and ethnic groups, age 21-40 with alcohol use disorder. Participants will be recruited through the Medical University of South Carolina's (MUSC) Addictions Research Center (ARC) Assessment Core. Inclusion/exclusion criteria are listed below:

General Inclusion/Exclusion Criteria

Inclusion Criteria

1. Age 21-40.
2. Subjects must be able to provide informed consent and function at an intellectual level sufficient to allow accurate completion of all assessment instruments.
3. Meets the DSM-5 criteria for current alcohol use disorder.
4. Reports drinking on average, at least 20 standard alcoholic drinks per week for at least the past three months.
5. Currently not engaged in, and does not want treatment for, alcohol related problems.
6. Lives within 50 miles of the study site.
7. Subjects must consent to random assignment.
8. Able to maintain abstinence for two days (without the aid of detoxification medications) as determined by self-report and breathalyzer measurements. Subjects must also have a negative breathalyzer urine drug screen at the study visit.
9. Subjects must consent to the study visit which includes an outpatient admission to the Addiction Sciences Division and completing one functional magnetic resonance imaging (fMRI) scanning session.

Exclusion Criteria

1. Currently meets DSM-5 criteria for any other psychoactive substance use disorder.
2. Is determined
3. Any psychoactive substance use (except marijuana and nicotine) within the last 30 days by self-report and urine drug screen. For marijuana, no use within the last seven days by verbal report and negative (or decreasing) urine THC levels.
4. Meets DSM-5 criteria for current major depression, panic disorder, obsessive-compulsive disorder, post-traumatic stress syndrome, bipolar affective disorder, schizophrenia, dissociate disorders, eating disorders, and any other psychotic disorder or organic mental disorder.
5. Has current suicidal ideation or homicidal ideation.
6. Has the need for maintenance or acute treatment with any psychoactive medication including anti-seizure medications and medications for ADHD.
7. Is currently taking medication known to affect alcohol intake (e.g., disulfiram, naltrexone, acamprosate, topiramate).

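### With 12 people per arm, no stratification by sex is described, and sex would enter the models only if it were tested and differed significantly between arms

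*Combined protocol and SAP*

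**What the plan says.** The Participants paragraph of the Approach sets the size: "Twenty-four individuals with AUD will be recruited". Its first inclusion criterion reads "male or female, any race or ethnicity; ages 21-40", and Section 1.1 repeats that both sexes are eligible. Neither place gives a quota or an expected number of women.

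The design paragraph after Study Visit Procedures gives the arms: "Intranasal OT (n=12) or PBO (n=12) sprays will be administered at 11:30 am, approximately 45 min prior to the scanning session". Randomisation is otherwise mentioned only in Section 1.1, inclusion item 7: "Subjects must consent to random assignment". No method, block size or stratification factor is described.

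Under Data Analyses, MIST connectivity is compared between arms with unpaired t-tests and the amygdala response to faces with one-way ANOVA. Craving and anxiety go into a linear mixed model for which no covariates are listed. The one provision for imbalance closes that section. It says "contrasts of other pertinent baseline characteristics will be performed between groups", followed by "If the groups differ significantly on any of these baseline characteristics, the corresponding variables will be used as covariates". The characteristics are not listed, sex is not named, and neither the test nor its level is stated.

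**The concern.** Each participant attends one scanning session after a single spray, so every oxytocin-placebo comparison is between different people. With 12 per arm, chance can leave the arms visibly different in sex mix. If sex is related to an outcome, that difference carries into the treatment contrast for that outcome, and the same realised allocation underlies all of them.

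The plan's safeguard works through a significance test on 24 people, which has little power to detect such a split. The shift in the result depends on how large the imbalance is and how strongly sex predicts the outcome, not on the p-value of the baseline comparison. The safeguard may not reach sex at all, because the plan does not say that sex is one of the characteristics to be compared. A data-driven trigger also leaves the final model unknown until the data are seen.

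**Working it through.** The documents state no imbalance probability, so there is no plan figure to reproduce. The two arms of 12 agree with the total of 24.

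**Inputs.** From the plan: 24 people, 12 per arm, both sexes. Assumed: the number of women K, shown over a range; a two-sided 0.05 level for the baseline test, as Fisher exact or uncorrected chi-square; and a sex effect of 0.5-1.0 SD.

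**Step 1. Chance of a split of 4 or more.** With exact 12 v 12 allocation, the number of women on oxytocin, X, is hypergeometric:

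P(X = x) = C(12, x) · C(12, K − x) / C(24, K), and the split is |x − (K − x)|.

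Example, K = 12. Splits of 4 or more are 8 v 4, 9 v 3, 10 v 2, 11 v 1 and 12 v 0, in either direction:

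2 × (495² + 220² + 66² + 12² + 1²) / 2,704,156 = 595,852 / 2,704,156 = 22.0%.

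**Step 2. Does the covariate rule act?** For 8 v 4, the uncorrected chi-square is 24 × (8×8 − 4×4)² / 12⁴ = 2.67, p = 0.10, and Fisher p = 0.22. The rule does not act. The table repeats both steps for each K. The p-values are for the smallest split that is at least 4, and the last two columns give the share of splits of 4 or more in which the rule would act.

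| Women (K) | P(split ≥ 4) | Smallest such split | Fisher p | Chi-square p | Acts, Fisher | Acts, chi-square |
|---|---|---|---|---|---|---|
| 6 | 15.5% | 4 | 0.155 | 0.059 | 8.9% | 8.9% |
| 7 | 6.9% | 5 | 0.069 | 0.025 | 6.7% | 100% |
| 8 | 19.3% | 4 | 0.193 | 0.083 | 14.1% | 14.1% |
| 9 | 8.9% | 5 | 0.089 | 0.035 | 10.5% | 100% |
| 10 | 21.4% | 4 | 0.214 | 0.098 | 16.9% | 16.9% |
| 11 | 10.0% | 5 | 0.100 | 0.041 | 12.3% | 100% |
| 12 | 22.0% | 4 | 0.220 | 0.102 | 17.8% | 17.8% |

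The figures mirror for 13 to 18 women. Odd counts give lower probabilities because the split is then odd, so the smallest one that qualifies is 5.

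For even counts the rule misses 100 − 17.8 = 82% to 100 − 8.9 = 91% of splits of 4 or more, with either test. For odd counts Fisher misses most of them and an uncorrected chi-square catches all.

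**Step 3. Number of women not fixed.** With K binomial at 25% to 50% women, P(split ≥ 4) is 9.6% to 15.2%. Among those splits the rule acts in about 15% (Fisher) or 41-46% (chi-square).

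**Step 4. Size of the shift.** Shift = (difference in women / 12) × sex effect. For 8 v 4: (4/12) × 0.5 = 0.17 SD, and (4/12) × 1.0 = 0.33 SD. The standard error of the arm difference is √(1/12 + 1/12) = 0.41 SD, where SD is the spread within sex.

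**Step 5. Can adjustment separate the two?** For 8 v 4 the correlation between sex and arm is (8×8 − 4×4)/144 = 1/3, so the variance inflation from a sex term is 1/(1 − 1/9) = 1.13. For 5 v 1 (K = 6) it is 1.17.

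**The case against.** The strongest reply is that randomisation already accounts for chance imbalance. Averaged over allocations the comparison is unbiased, and the shift computed here stays below one standard error even at the top of the assumed range. That stands, and it limits the point to precision and to interpreting the one allocation that the trial will have.

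Much of the outcome set is also built from within-person contrasts: stress against control for MIST connectivity, fearful against neutral faces, and serial ratings in a mixed model. These remove stable level differences between people. They do not remove a sex difference in reactivity, and resting connectivity has no such contrast. The documents give no sex effect on any outcome, so the shift is conditional on an assumption.

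One could also ask why sex, and not recent drinking or childhood trauma, which are measured too. The documents do not rank them. Sex is convenient because it is binary and known before allocation.

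Two stronger readings are tempting. A reader might infer that allocation is unstratified. The documents are silent on the method, so one can say only that no stratification is described. A reader might also infer that an 8 v 4 split could not be told apart from a drug effect. That is wrong: a sex term separates the two at a variance inflation of about 1.13.

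**Conclusion.** The concern holds as a minor point. No stratification is described, the stated tests are unadjusted, and the significance-triggered rule is a weak safeguard that may not cover sex.

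The chance of a split of 4 or more ranges from 7% to 22% for 6 to 12 women, depending largely on whether the count is even or odd, and is about 10-15% averaged over the assumed mix. It would be too strong to say that the rule almost never acts. That describes splits of exactly 4. For splits of 4 or more with even counts it acts in 9-18%, and for 7, 9 or 11 women an uncorrected chi-square would catch them all.

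These results assume exact 12 v 12 allocation without stratification, a 0.05 level, and the two tests named; the plan states neither level nor test. The shift of 0.17-0.33 SD also rests on the assumed sex effect.

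**What to change.** Pre-specify sex as a fixed term in every oxytocin-placebo model, whatever a baseline test shows: the second-level imaging models, the region-of-interest ANOVA, and the mixed models for craving and anxiety. This step alone removes the dependence on the significance trigger for sex.

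In addition, state the randomisation method and allocate in small permuted blocks stratified by sex. Blocks of 4 cap the difference in women between arms at 2, and blocks of 2 cap it at 1, so a split of 4 cannot occur.

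The cost is 1 df per model (of 22 in a two-arm comparison of 24 people), two allocation lists instead of one, and arms that may end slightly unequal. An incomplete last block in both strata can give 11 v 13 with blocks of 2 and up to 10 v 14 with blocks of 4. Blocks of 2 hold the balance more tightly but make the next assignment easier to predict if the blind is broken for one member of a pair.

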5. DATA AND SAFETY MONITORING PLAN (DSMP)

5.1 Summary of the Protocol

The primary objective of this proposal is to identifying the neurobiologic substrates of social stress in individuals with alcohol use disorder. Individuals with alcohol use disorder will receive either intranasal oxytocin (24 IU) or a placebo spray prior to participating in a single fMRI scanning session. During the scanning session participants will complete the Montreal Imaging Stress Task, a Facial Affect Recognition Task, and a resting state scan. The primary outcomes of interest are (1) corticolimbic functional connectivity at rest; (2) corticolimbic functional connectivity during the MIST and (3) subjective anxiety and craving responses to the MIST.

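### The face task as specified has no neutral-face blocks, so its fearful-versus-neutral contrast of interest cannot be estimated

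*Combined protocol and SAP*

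**What the plan says.** In the Approach, the paragraph on the Implicit Facial Affect Recognition Task describes faces "expressing three different categories of emotion; fear, anger, and happiness". The next sentence reads "Neutral faces will also be presented (Figure 5"), without saying in what role; the figure is not in the text available for review. Every block holds 56 faces of a single emotion and a single gender, and from this the paragraph derives its counts: "so there will be 6 pseudorandomly ordered task blocks (3 emotions x 2 genders) and 7 rest blocks (27.5 sec each"), the rest blocks being crosshair fixation. Within a task block, "each emotional face will be presented for 33 msec. followed by a neutral face mask (from a different individual) for 167 msec", and then a blank screen. This mask is the only use of neutral faces that the paragraph describes.

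In Data Analyses, the first-level model for this task is a GLM "with each emotion (described below) modeled as a box-car function", plus a regressor for the response period and six motion parameters. The outcome is stated as follows: "The percent signal change between the fearful and neutral conditions (contrast of interest) will be calculated for each participant". Left-amygdala values are compared between the oxytocin and placebo groups, the right amygdala and insula are secondary regions, and a happy-minus-neutral contrast is mentioned for possible later work.

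Section 5.1 does not list the face task among the outcomes that matter most: "The primary outcomes of interest are (1) corticolimbic functional connectivity at rest; (2) corticolimbic functional connectivity during the MIST", and, third, anxiety and craving responses to the MIST.

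**The concern.** The analysis treats neutral as a condition with its own response. The design, as counted, contains no block in which neutral faces are the target. Either neutral blocks were intended and the counts leave them out, or neutral faces are only masks and the contrast has nothing to subtract.

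What is at stake is whether the only contrast planned for this task can be computed at all. If the task is programmed from the Approach text, what remains is fear versus crosshair or fear versus another emotion. Fear versus crosshair does not separate a response to fear from the general response to faces and visual stimulation. An analysis choice can be revisited after the data are in; a missing stimulus condition cannot.

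**Working it through.** **Inputs.** From the face-task paragraph: 3 emotions, 2 genders, 6 task blocks, 7 rest blocks of 27.5 s, 56 faces per block, 33 ms face, 167 ms mask, 291 ms blank, and a 5 s response after each task block. From the BOLD-fMRI procedure: TR 2 s, assumed to apply to this task too. From Participants: 24 subjects.

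**The plan's own figures.**
- Task blocks: 3 × 2 = 6, as stated.
- Rest blocks: 6 + 1 = 7, as stated, if rest comes before, between and after the task blocks (an assumption about the order).
- Block length: 56 × (33 + 167 + 291) ms = 56 × 491 ms = 27.496 s, against the stated 27.5 s. The faces fill the block, so the 5 s response comes on top.
- Run length: 6 × (27.5 + 5) + 7 × 27.5 = 195 + 192.5 = 387.5 s, or 193.75 TRs.

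The counts therefore agree with each other and leave no room for a fourth category, which would need 4 × 2 = 8 task blocks.

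**Time per condition as written.** Fear: 2 × 27.5 = 55 s. Neutral as target: 0 s. Neutral as mask: 56 × 167 ms = 9.35 s in each of the 6 task blocks, whatever the emotion.

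**Estimability with no neutral block.** The neutral column of the design matrix is zero. Any constant can be added to its coefficient without changing the fitted values, so fear minus neutral is not determined.

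**Estimability with the mask taken as neutral.** The mask occurs in every task block, so at block level its column satisfies mask = fear + anger + happy. Adding δ to the mask coefficient and subtracting δ from the three emotion coefficients leaves the fit unchanged, yet shifts fear minus mask by −2δ. Again it is not determined. The plan does not propose this regressor; it is included because it is the natural reply.

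Neither argument depends on block order, the response function or the motion terms.

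**Numerical check.** Box-cars were convolved with a double-gamma response function at TR 2 s, with a response regressor, an intercept and one assumed block order. Six simulated motion columns were included except in the mask row.

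| Design | Rank / columns | Fear − neutral |
|---|---|---|
| 6 task blocks, empty neutral column | 11 / 12 | not estimable |
| 6 task blocks, mask as neutral (no motion columns) | 5 / 6 | not estimable |
| 8 task blocks including neutral | 12 / 12 | estimable |
| 6 task blocks of fear, happy, neutral | 11 / 11 | estimable |

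In the first design, happy minus neutral is also not estimable, while fear minus rest and fear minus anger are.

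**Length if neutral blocks are added.** With 8 task and 9 rest blocks: 8 × 32.5 + 9 × 27.5 = 260 + 247.5 = 507.5 s, or 253.75 TRs. The increase is 120 s, or 60 volumes. If the rest blocks stay at 7: 260 + 192.5 = 452.5 s, an increase of 65 s.

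**The case against.** The best reply is that this is a slip in a count. The sentence about neutral faces directly follows the list of emotions, before masks are introduced, which suggests a further stimulus category. The analysis section then uses neutral as a comparator twice. On that reading the two sections agree on intent, the error is the parenthesis giving three emotions by two genders, and the missing figure might show as much. This is plausible, and the documents do not exclude it. It still means that the stated counts are wrong, and those counts are what a programmer would follow.

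A second reply is that the list of categories may be wrong instead: with fear, happy and neutral, six blocks suffice and the contrast is estimable. No anger contrast is planned, so this is not far-fetched. But the text names anger explicitly, so this too is a way of correcting the text, not a reading under which the text is right.

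Two further points stand. The rank calculation only confirms that a condition without blocks has no estimate, and the longer run time belongs to one possible remedy rather than to the plan. The consequence is also limited: the face task appears in neither stated aim (Data Analyses attaches it to Specific Aim 2, but Aim 2 concerns resting-state connectivity) and is not among the primary outcomes in section 5.1.

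**Conclusion.** The design and analysis descriptions of the face task are inconsistent, and this should be fixed before scanning. Under the counts as written there are 55 s of fear and 0 s of neutral targets, and the fearful-minus-neutral contrast is not estimable in any participant. The group test on it, the right-amygdala and insula analyses, and the possible happy-minus-neutral contrast fail with it.

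That the passages conflict is certain. Non-estimability is conditional on the task being run to the stated 6 and 7 blocks with fear, anger and happiness as the categories; the documents do not show which version was intended or programmed. The MIST, resting-state, craving and anxiety analyses are unaffected.

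**What to change.** Check the stimulus script against the protocol, then make the two sections agree:

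- **Neutral blocks are already in the script.** Correct the block counts, and the category list if that is where the slip lies. This is a text change with no scan time beyond the intended task.
- **They are not in the script.** Add one neutral-target block per gender, with a neutral face masked by a different neutral face. State 8 task blocks (4 categories × 2 genders) and, if rest keeps alternating with task, 9 rest blocks. The cost is a script edit, a short amendment and 120 s per participant, or 24 × 120 s = 48 min in total. With rest held at 7 blocks it is 65 s each, or 24 × 65 s = 26 min. Replacing the anger blocks with neutral ones adds no scan time but gives up a listed emotion.
- **Neutral blocks will not be acquired.** Redefine the contrast before any data are seen, for example fear versus crosshair, and state that it no longer isolates fear against neutral faces.

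Wherever neutral blocks are run, name neutral as its own regressor in the first-level GLM in Data Analyses.
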